1.1 Statistical Analysis

Statistical analyses will be performed by an independent statistician (to be determined). Means and standard deviations across all participants will be calculated for each outcome measure and baseline demographic characteristics. Baseline data will be presented as descriptive data using measures of central tendency. Alpha will be set at 0.05 for all testing.

The primary focus of this study is the feasibility of the intervention. The use of a delayed-control design will be implemented to secondarily assess the efficacy of the intervention. Feasibility outcomes will be reported via summary statistics with a focus on the primary outcomes listed above.

1.1.1 Primary Statistical Testing:

Performance of the modification at the primary end point (6-week follow up) will be examined as outlined in comparison 1 below. All other outcomes measured at baseline, follow up and retention will also be examined using the comparisons below but are considered secondary to the feasibility and performance outcomes.

The statistical comparisons for laboratory-measured outcomes in descending order of priority:

- 1) Between group change at week 6 and week 10 (Delayed Group Secondary Baseline vs Immediate Group Follow up) assessed using an analysis of covariance for the difference in follow-up values while adjusting for baseline values.
- 2) Within-subject comparison of the Delayed Group intervention period, using the Delayed Group as their own control (Delayed Group Follow up vs Delayed Group Secondary Baseline) assessed using a mixed effects model with the participant as the random effect to account for the within-subject nature of the data.
- 3) Within-subject comparison of both groups' data from the intervention (excluding the Delayed Group control period) assessed using a repeated measures analysis of variance across baseline, follow up, and retention timepoints.

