- H4: Significant improvements in pain and physical function will be reported between the Immediate Group and Delayed Group at week 6 of the study (Follow up for the Immediate

Group and the secondary baseline for the Delayed Group). We also expect to see significant within-group improvements in pain and physical function in the Delayed Group when comparing their change from baseline to secondary baseline (control) with their change from secondary baseline to follow up (intervention).

H5: Significant decreases in the knee adduction moment late stance peak and impulse will be exhibited between the Immediate Group and Delayed Group at week 6 of the study (Follow up for the Immediate Group and the secondary baseline for the Delayed Group). We also expect to see significant within-group decreases of the knee adduction moments in the Delayed Group when comparing their change from baseline to secondary baseline (control) with their change from secondary baseline to follow up (intervention). Knee flexion moment peak and impulse will not significantly increase for these same comparisons.

4 Methods and Approaches

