4.2.2 Sample Size Calculation

This study is primary focused on investigating the feasibility of delivering the gait modification using a telerehabilitation model and using wearable sensors to monitor performance. Past feasibility or pilot studies using gait modification for knee OA have included 10-20 participants [31, 32]. Indeed, it is also a feasible recruitment goal that our research group has achieved in previous pilot testing with this population [31]. The primary statistical test will compare the between-group difference in FPA at follow up using an analysis of covariance. With a large effect size expected ($f= 1.0$), power of 80%, alpha of 5%, and two groups with three covariates (two stratification variables and baseline FPA) we require a minimum of 14 participants. Given we are also interested in our secondary analyses, and to account for dropout, we will be recruiting a total of 15 participants per group for a total of 30.

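### For pain, function and joint moments the SAP ranks three comparisons but does not say which carries the efficacy conclusion, and two of them can reach significance from natural change alone

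*SAP*

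**What the plan says.** SAP 1.1 sets one threshold: "Alpha will be set at 0.05 for all testing". SAP 1.1.1 then lists three comparisons for laboratory-measured outcomes, ranked from highest to lowest priority:

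1. A between-group analysis of covariance, Immediate Group follow-up against Delayed Group secondary baseline, adjusted for baseline.
2. A mixed model within the Delayed Group, follow-up against secondary baseline.
3. A within-subject analysis of both groups' "data from the intervention (excluding the Delayed Group control period) assessed using a repeated measures analysis of variance", over baseline, follow-up and retention.

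Performance of the modification at the 6-week end point is assigned to comparison 1. For the rest, "All other outcomes measured at baseline, follow up and retention will also be examined using the comparisons below", and these outcomes are labelled secondary to feasibility and performance. The SAP text available for review has no rule making a lower comparison depend on a higher one, and does not say how to read comparisons 2 and 3 when comparison 1 is null.

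The protocol expects significance from more than one source. H4 (section 3.1) predicts a between-group difference at week 6 and adds "We also expect to see significant within-group improvements in pain and physical function in the Delayed Group"; H5 does the same for the knee adduction moment. Section 1 describes effectiveness as a comparison of patient-reported outcomes and knee moments before and after the program, whereas SAP 1.1 says that the delayed-control design is there to assess efficacy, secondarily.

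**The concern.** The priority order has no consequence for testing or interpretation. Suppose that for pain comparison 1 gives p = 0.30 and comparison 3 gives p = 0.01. The plan does not say whether that is evidence of efficacy, and the before-and-after wording in protocol section 1 would let an author say that it is.

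The comparisons are not equally protected. In comparison 1 both groups have lived through the same six weeks, so natural change cancels. In comparison 3 the control period is removed by design, so any natural improvement is counted with the intervention, in the largest sample of the three. Comparison 2 has the same weakness in a smaller sample. The SAP calls the Delayed Group its own control there, but the contrast it specifies is follow-up against secondary baseline. H4 and H5 describe something else: change during the intervention period set against change during the waiting period.

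Natural change is plausible for self-reported pain. Protocol 4.2.1 requires pain of at least 3/10 at entry, which invites regression to the mean, and participants know when they are receiving the intervention. At stake is whether the protection that the delayed-control design provides reaches the reported conclusion.

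**Working it through.** **The plan's own figure.** Protocol 4.2.2 sizes comparison 1 for foot progression angle (FPA) only: "The primary statistical test will compare the between-group difference in FPA at follow up using an analysis of covariance", with f = 1.0, "power of 80%, alpha of 5%, and two groups with three covariates". Using a noncentral F with noncentrality f²N and N − 2 − 3 error degrees of freedom, N = 11 gives 78.8% power, N = 12 gives 84.2% and N = 14 gives 91.3%. The stated minimum of 14 is therefore sufficient. It says nothing about pain or joint moments: f = 1.0 for two groups is d = 2.0.

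**Inputs for the error rates.** From the documents: 15 per group, alpha 0.05, and the visit times in protocol Table 1. Assumed: outcome SD 1, equal correlation ρ of 0.5 or 0.7 between visits, no dropout, no intervention effect, and natural change s in SD units. The change is either linear (s per 6 weeks) or a single shift after first baseline.

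**Comparison 1.** Both groups are measured at week 6 and have shifted by the same amount, so s cancels and the rate stays at about 5%.

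**Comparison 2.** This is equivalent to a paired t test with 14 degrees of freedom and noncentrality s√15 / √(2(1 − ρ)).
- Linear, s = 0.2: 0.775 (ρ = 0.5) or 1.00 (ρ = 0.7), giving 11% and 15%.
- Linear, s = 0.1: 0.387 or 0.50, giving 7% and 8%.
- One-off shift: both visits fall after it, so about 5%.

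**Comparison 3.** The three-visit F test has 2 and 58 degrees of freedom (critical value 3.16) and noncentrality λ = 30 × Σ(visit mean − overall mean)² / (1 − ρ). Counted from the start of the intervention, the visits are at 0, 6 and 10 weeks in both groups.
- Linear, s = 0.2: relative means 0, 0.2, 0.333; sum of squares 0.0563; λ = 30 × 0.0563 / 0.5 = 3.38 or / 0.3 = 5.63; significant in 34% and 53%.
- Linear, s = 0.1: sum of squares 0.0141; λ = 0.84 or 1.41; 12% and 16%.
- One-off, s = 0.2: Immediate 0, 0.2, 0.2 and Delayed 0.2, 0.2, 0.2, so pooled means 0.1, 0.2, 0.2; sum of squares 0.00667; λ = 0.40 or 0.67; 8% and 10%. This case is slightly approximate because the group profiles differ.

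In summary, with no intervention effect:

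| Natural change | Comparison 1 | Comparison 2 | Comparison 3 |
|---|---|---|---|
| None | 5% | 5% | 5% |
| One-off 0.2 SD | 5% | 5% | 8-10% |
| Linear 0.1 SD per 6 weeks | 5% | 7-8% | 12-16% |
| Linear 0.2 SD per 6 weeks | 5% | 11-15% | 34-53% |

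Simulation of the full design agrees within sampling error apart from one run at the upper end for linear 0.1 SD: comparison 3 was significant in 8-11% (one-off 0.2), 11-18% (linear 0.1) and 33-53% (linear 0.2).

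**Discordance.** In simulation, comparison 3 is significant while comparison 1 is not in 3-4% of trials with no change over time, 7-9% with a one-off 0.2 SD shift and 31-49% with linear drift of 0.2 SD.

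**Any of the three.** Independent tests would give 1 − 0.95³ = 14.3%. With the overlapping data and no drift, simulation gives 12-13%.

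**Would a smaller alpha help?** Not with the main problem. A threshold of 0.05/3 = 0.0167 deals with multiplicity, but comparison 3 would still be testing change without a control.

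**The case against.** The other side has four good points.

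First, the scope is narrow. The primary tested outcome, 6-week performance, goes to comparison 1; feasibility is reported by summary statistics; and the trial is exploratory. A reader might infer that every outcome, including the primary one, gets three attempts at 0.05. The SAP does not support that. Only secondary outcomes are affected.

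Second, the SAP nowhere says that comparison 3 will be presented as efficacy. It is ranked last and labelled within-subject, no hypothesis depends on it, and it is the only one of the three that describes retention across both groups. This stands: the plan fails to prevent the misuse but does not announce it.

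Third, the three tests ask different questions, so the 12-13% figure is a false-positive rate for efficacy only if all three are read as efficacy claims. Strict gatekeeping of every secondary test in a 30-person exploratory trial is more than is needed. This also stands.

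Fourth, the 34-53% result depends on one assumed drift size and shape, with drift continuing through retention. Smaller or one-off changes give 8-16%. For joint moments the basis for drift is weaker than for pain, since protocol 4.3.4 B constrains walking speed at follow-up to within 5% of baseline.

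What remains is that discordant results are foreseeable and the plan does not say how to read them. For an assumed true effect of 0.5 SD, comparison 1 with 15 per group has noncentrality 0.5 / √(1 − ρ²) × √7.5 = 1.58 or 1.92 on 27 degrees of freedom, which is 33-46% power. A null comparison 1 beside a significant comparison 3 is therefore quite possible even if the intervention works.

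**Conclusion.** The concern holds for the secondary efficacy outcomes. The plan ranks three comparisons, tests each at 0.05, and leaves open which one supports a statement about efficacy, although two of them have no control for natural change. With no intervention effect, comparison 3 is significant in anything from about 5% of trials (no change over time) to 34-53% (linear drift of 0.2 SD per 6 weeks), while comparison 1 holds near 5%. The range rests on assumed drift and on a visit correlation of 0.5 to 0.7; the documents give neither.

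It would go too far to treat the top of that range as the trial's error rate, or to call comparison 3 the test most likely to be significant: without an intervention effect, that is true only if there is natural change. The main problem is bias from the missing control, more than the number of tests. It should be corrected, but it does not threaten the feasibility conclusions or the primary performance test.

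**What to change.** In SAP 1.1.1, state that for each secondary outcome the conclusion on efficacy rests on comparison 1 at week 6. Week 6 has to be named: the SAP applies comparison 1 to weeks 6 and 10, but protocol Table 1 has no Delayed Group visit at week 10.

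Report comparisons 2 and 3 as supportive estimates with 95% confidence intervals, described as change over time including retention. State that they will not be presented as evidence of an intervention effect when comparison 1 is not significant.

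Two passages need aligning. Protocol section 1 should no longer imply that a before-and-after comparison establishes effectiveness. The primary pain outcome also has to be reconciled before a pain conclusion is tied to it: protocol 4.4.2 F names the WOMAC pain subscale, while the questionnaire lists in 4.3.4 A name the NRS and KOOS.

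The cost is wording. Sample size, visits and data collection are unchanged. Fewer results may be called significant, and the within-group part of H4 and H5 becomes supportive. Given the limited power of comparison 1 for these outcomes, a null result should be reported with its interval and not as absence of effect. Multiplicity across the many secondary outcomes is a separate matter that this change does not settle.

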4.2.1 Inclusion and Exclusion Criteria

All eligible participants will: 1) be 50 years of age or greater, 2) exhibit signs of tibiofemoral OA (a score of ≥ 2 on the Kellgren and Lawrence (KL) grading scale [47]) predominantly in the medial compartment, 3) self-reported knee pain $\geq 3 / 10$ on a numerical rating scale of pain (NRS; 0 = “no pain” and 10 = “worst pain imaginable”) during most days of the previous month, 4) are comfortable walking intermittently for 30 minutes, and 5) fit into the available sizes of sensorized shoes (sizes spanning US women’s 5 to men’s 13).

Exclusion criteria include: 1) any knee surgery or intraarticular injections within the past 6 months, 2) a history of joint replacement surgery or high tibial osteotomy, 3) current or recent (within 6 weeks) corticosteroid injections, 4) use of a gait aid, 5) currently on a wait list for joint

replacement surgery or high tibial osteotomy, 6) any inflammatory arthritic condition, and 7) any other conditions that may affect normal gait or participation in an aerobic exercise program. Additionally, potential participants will undergo an initial gait screening similar to a recent study [48] (details are outlined below – section 4.3.1-A), with the goal of identifying participants who are capable of reducing their KAM magnitude when FPA is modified. This gait screen will examine changes in knee load while walking with increased toe-in and toe-out, compared to natural FPA. Those who cannot elicit a reduction in KAM impulse $\geq 2\%$ when FPA is changed by 10° in either direction will be excluded from the study as they would be considered non-responders.

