4.3.3 Randomization and Study Groups

Participants will be randomly allocated to either an Immediate Group or a Delayed Group after completing the baseline collection. The Immediate Group will be introduced to the gait modification and sent home with the sensorized shoes to begin the intervention as described below. The Delayed Group will schedule their

[figure not shown]

Figure 1. Sensor module construction and placement within the shoe. IMU, inertial measurement unit (accelerometer and gyroscope).

secondary baseline for 6 weeks in the future and receive no intervention for that time period. After the 6 weeks of no intervention, the Delayed Group participants will return to the lab to receive their secondary baseline assessment and begin the intervention thereafter. We will use a variable block size stratified (KL grade and sex) randomization sequence with allocations sealed in envelopes, kept by [name], and revealed after the baseline data collection is complete.

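### SAP comparison 1 adjusts for baseline only, although the protocol stratifies by KL grade and sex and sizes the ANCOVA with both; adding them costs almost nothing and may help the secondary tests

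*SAP*

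**What the plan says.** - **SAP 1.1.1, comparison 1** (first in priority): the group contrast is "assessed using an analysis of covariance for the difference in follow-up values while adjusting for baseline values". The SAP text available for review names no stratification factor as a term in this model.
- **SAP 1.1.1, scope:** "All other outcomes measured at baseline, follow up and retention will also be examined using the comparisons below". The same model therefore serves the secondary outcomes.
- **Protocol 4.2.2:** the primary FPA test is an ANCOVA with "two groups with three covariates (two stratification variables and baseline FPA"). At f = 1.0, 80% power and 5% alpha it gives a minimum of 14. The trial recruits 30, citing dropout and the secondary analyses.
- **Protocol 4.3.3:** "We will use a variable block size stratified (KL grade and sex) randomization sequence".
- **Protocol 4.2.1:** eligibility requires "a score of ≥ 2 on the Kellgren and Lawrence (KL) grading scale", which allows up to three KL levels. The documents do not say how the grades are grouped for stratification.
- **Protocol 3.1, H4:** "Significant improvements in pain and physical function will be reported between the Immediate Group and Delayed Group at week 6 of the study". H5 makes the matching prediction for the knee adduction moment.

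**The concern.** The protocol sizes one model and the SAP describes another. The SAP does not exclude the strata. But it gives the analysis to a statistician not yet appointed, and the natural reading of its wording is a model with group and the baseline value of the outcome. The covariate set is then open to choice after the data are seen.

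Stratified randomisation balances the arms on KL grade and sex, which lowers the true variance of the group difference when those factors are prognostic. A model without them leaves their contribution in the residual variance. Its standard errors are then too large and the test is conservative. Type I error is not inflated. What is at stake is power in the H4 and H5 between-group tests, for which the protocol states no power and where effects may be well below f = 1.0.

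**Working it through.** **1. The plan's own figure.** Noncentral F with 1 numerator df, denominator df = N − 2 − c (c = covariate df) and λ = f²N. With f = 1.0, c = 3 and alpha 5%:

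- N = 11: 78.8%
- N = 12: 84.2%
- N = 14: 91.3%

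The smallest N for 80% is 12, close to the stated 14 and on its safe side. With c = 4 (KL grade in three levels) it is also 12. The sizing stands with the strata included.

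**2. Primary FPA test, f = 1.0.** The 24 completers are an assumption; the protocol gives no dropout rate.

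| N | c = 1 (baseline only) | c = 3 (KL in 2 levels) | c = 4 (KL in 3 levels) |
|---|---|---|---|
| 30 | 99.954% | 99.951% | 99.949% |
| 24 | 99.66% | 99.63% | 99.61% |

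**3. Secondary outcomes, by formula.** Let d be the effect in SDs after baseline adjustment, so f = d/2 for two equal groups, and let R² be the share of post-baseline variance explained by the strata. Then λ = f²N/(1 − R²). For N = 30 and d = 0.8, f²N = 0.16 × 30 = 4.8.

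- Baseline only: λ = 4.8, df 27, power 56.1%.
- Strata added, R² = 0: λ = 4.8, power 55.8% (df 25) or 55.7% (df 24).
- Strata added, R² = 0.1, 0.2, 0.3: λ = 5.33, 6.00, 6.86; power 60.3%, 65.4%, 71.1% (df 25).

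This ignores chance imbalance from incomplete blocks and does not show the conservatism of the baseline-only test, so it was simulated.

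**4. Secondary outcomes, by simulation.** N = 30, d = 0.8, 20,000 trials per cell (Monte Carlo SE about 0.35 points for power, 0.15 for type I error). Assumed: equally likely KL levels, random blocks of 2 and 4, and KL grade and sex sharing R² equally.

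| R² | KL levels | Power, baseline only | Power, with strata | Type I error, baseline only |
|---|---|---|---|---|
| 0% | 2 | 55.1% | 54.5% | |
| 0% | 3 | 54.4% | 53.2% | |
| 10% | 2 | 54.6% | 58.4% | 4.2% |
| 10% | 3 | 55.1% | 57.9% | 3.8% |
| 20% | 2 | 54.5% | 63.0% | 3.2% |
| 20% | 3 | 54.4% | 62.3% | 3.2% |
| 30% | 2 | 55.1% | 69.4% | 2.2% |
| 30% | 3 | 54.5% | 68.4% | 2.5% |

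Type I error with the strata included was 4.6-5.1%. The mean standard error falls by about 4-5%, 10% and 16% at R² of 10%, 20% and 30%, close to 1 − √(1 − R²) = 5.1%, 10.6% and 16.3%.

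**5. Sensitivity** (8,000 trials per cell), baseline only against strata added:

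- R² = 30%, KL in two levels: 21.9% against 34.2% at 0.5 SD; 76.2% against 86.6% at 1.0 SD; 43.8% against 57.6% at 0.8 SD with 24 completers.
- R² = 0, KL in three levels: 73.8% against 72.4% at 1.0 SD; 44.2% against 42.5% at 0.8 SD with 24 completers.

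Unequal KL shares (grades 2, 3 and 4 at 40%, 35% and 25%; 6,000 trials per cell; KL as 1 df) give the same picture at 0.8 SD: 54.9% to 58.4%, 55.0% to 63.1% and 54.7% to 68.7% at R² of 10%, 20% and 30%.

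**The case against.** The strongest reply is that the gain rests on assumed values. Nothing in the documents supports strata that explain 10-30% of the variance left after baseline adjustment, and baseline pain or knee moment may already carry much of any KL or sex effect. Between 0 and 5% there is little to win. Simulated change in power at 0.8 SD (12,000 trials per cell, same design assumptions):

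| N | KL levels | R² 0% | R² 2% | R² 5% |
|---|---|---|---|---|
| 30 | 2 | −0.2 | +0.3 | +1.3 |
| 30 | 3 | −1.0 | −0.4 | +0.5 |
| 24 | 2 | −1.1 | 0.0 | +1.2 |
| 24 | 3 | −1.9 | −1.0 | 0.0 |

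With three KL levels, break-even is thus about 3-4% at N = 30 and about 5% at N = 24. The formula puts it lower, at 0.6-1.0% and 1.0-1.7%, because it ignores chance imbalance. This stands: the gain is conditional, and the change is nearly free but not free.

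Other points are fair but do not remove the concern:

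- The SAP refers to primary outcomes listed earlier, and in the documents available these appear only in Protocol 4.4.1. It may be meant to be read with the protocol, which already names the covariates. Even so, 4.2.2 does so for FPA only, and the SAP's own model statement is what an analyst would follow.
- Extending the strata to pain, function and knee moments is therefore a recommendation; the conflict between the documents concerns FPA alone.
- The trial is a feasibility study with efficacy secondary. It nevertheless plans formal tests at 0.05, and H4 and H5 predict significant differences.

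**Conclusion.** The concern holds. The sample-size section and SAP comparison 1 describe different covariate sets, and the SAP model leaves out the factors used to stratify randomisation.

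The primary FPA conclusion is not at risk: any difference in power is below 0.1 points, and the baseline-only test does not inflate type I error. For the secondary between-group tests at N = 30, adding the strata gains 2 to 14 points over effects of 0.5 to 1.0 SD if they explain 10-30% of post-baseline variance. It changes little at up to 5%, and loses 0.3 to 1.4 points if they explain nothing. With 24 completers at 0.8 SD, the gain is 2 to 14 points, and the loss at zero prognostic value about 1 to 2.

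Effect size, prognostic strength, KL distribution, block sizes and number of completers are all assumed. The case for aligning the two texts does not depend on them. It is an inexpensive correction that should be made, but it does not threaten the trial's validity.

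**What to change.** Write SAP comparison 1 as: follow-up value = group + baseline value of the outcome + KL grade + sex, with the strata coded as in the randomisation. Apply it to FPA and to every secondary between-group outcome. State in the SAP how KL grade is grouped for stratification, and fix before the data are seen how a sparse KL level will be merged.

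The cost is SAP wording, plus two of the 27 residual degrees of freedom at N = 30 if KL grade has two levels, or three if it has three. Both variables are already collected for randomisation. The sample size needs no restatement, since Protocol 4.2.2 already counts the stratification variables.

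### Comparison 3 uses repeated measures ANOVA, which keeps only participants with all three visits: this costs precision, and overstates change if missing retention depends on response

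*SAP*

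**What the plan says.** SAP section 1.1.1 introduces its list this way: "The statistical comparisons for laboratory-measured outcomes in descending order of priority". Comparison 1 is a between-group analysis of covariance and carries the test of modification performance at 6 weeks. Comparison 2, in the Delayed Group alone, is "assessed using a mixed effects model with the participant as the random effect to account for the within-subject nature of the data". Comparison 3 takes both groups' intervention data, leaves out the Delayed Group's waiting period, and is "assessed using a repeated measures analysis of variance across baseline, follow up, and retention timepoints". From Protocol Table 1, I read the three visits as weeks 0, 6 and 10 for the Immediate Group and weeks 6, 12 and 16 for the Delayed Group.

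Protocol section 4.2.2 recruits 30 partly to allow for dropout but gives no rate. The SAP text available for this review starts at section 1.1. It contains no rule for missed visits, no imputation, no definition of an analysis set and no sensitivity analysis.

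**The concern.** Classical repeated measures ANOVA needs a value at every visit for each participant, and it assumes sphericity. A participant who attends follow-up but not retention is removed altogether, although the baseline-to-follow-up change was observed.

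Comparison 3 has twice the participants of comparison 2 and one more visit, so it has more chances for a missed visit. Yet it is given the method that cannot use incomplete records, while comparison 2 already has a mixed model. Comparison 3 is also the only analysis that pools both groups' intervention data and follows participants through to retention. At stake are the precision of that pooled estimate and, if missing visits are related to response, its accuracy.

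**Working it through.** **The plan's own figure.** The documents size only comparison 1: "With a large effect size expected ($f= 1.0$), power of 80%, alpha of 5%, and two groups with three covariates", from which "we require a minimum of 14 participants". With noncentrality f² × N, 1 numerator and N − 2 − 3 denominator degrees of freedom, power is 84.2% at N = 12 (the smallest N reaching 80%) and 91.3% at N = 14. With 2 numerator degrees of freedom, 14 is the smallest N (80.9%). The figure reproduces within two participants, but it has no bearing on comparison 3, for which no sample size, power or dropout figure is given.

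**Participants left.** Input: N = 30 (Protocol section 4.2.2). The missing-visit rates are assumptions.

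| Pattern of missing visits | Calculation | With all three visits |
|---|---|---|
| 10% miss each later visit, independently | 30 × 0.9² | 24.3 |
| 15%, independently | 30 × 0.85² | 21.7 |
| 20%, independently | 30 × 0.8² | 19.2 |
| The same 10% miss both | 30 × 0.9 | 27 |

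In the first row, 30 × 0.9 × 0.1 = 2.7 participants have an observed follow-up change that is discarded. In the last row those lost have only a baseline, so no observed change is thrown away.

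**Bias.** Assumptions: pain means 5, 4 and 4 (true change -1.0 at both later visits), SD 2, correlation 0.6 between all visits, and 18% missing retention. The log-odds of missing retention rise with each point of worse observed baseline-to-follow-up change. Large-sample simulation, participants with all three visits only:

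| Log-odds per point | Follow-up change | Retention change |
|---|---|---|
| 0 (unrelated to response) | -1.00 | -1.00 |
| 0.2 | -1.11 | -1.06 |
| 0.5 | -1.26 | -1.12 |
| 0.8 | -1.36 | -1.18 |

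The SD of a change is √(2 × 2² × (1 − 0.6)) = 1.79. The log-odds therefore correspond to odds ratios per SD of change of exp(0.2 × 1.79) = 1.4, exp(0.5 × 1.79) = 2.4 and exp(0.8 × 1.79) = 4.2. The standard error of a mean change in 30 people is 1.79 / √30 = 0.33. The retention overstatement (0.06 to 0.18) stays below one standard error; the follow-up overstatement (0.11 to 0.36) reaches about one at the strongest setting.

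**Which mixed model.** With equal correlations, a random intercept and an unstructured covariance both recover -1.00. With unequal correlations (assumed: baseline–follow-up 0.5, baseline–retention 0.4, follow-up–retention 0.85) and 20% missing retention, the retention change was:

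| Log-odds per point | Before dropout | Completers | Random intercept |
|---|---|---|---|
| 0.5 | -1.00 | -1.34 | -1.15 |
| 0.8 | -0.97 | -1.44 | -1.19 |

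The random intercept leaves 0.15 / 0.34 = 44% and 0.22 / 0.47 = 47% of the bias. An unstructured covariance gives about -1.00.

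**The case against.** The strongest reply has four parts.

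- **Listwise deletion is inferred.** The SAP does not say that incomplete participants are dropped. That follows from the named method together with the absence of a missing-visit rule in the text available. This stands as a caveat, and a stated rule would settle it.
- **The bias is conditional.** A reader might infer that non-responders are the people who skip retention, so that completers must overstate benefit. Nothing in the documents supports that. Protocol section 4.2.2 mentions dropout without a rate or a cause. If missed visits are unrelated to response, only precision is lost. This stands.
- **The gain may be small.** If the same people miss both later visits, they contribute only a baseline and a mixed model recovers little. The benefit is confined to people who attend one later visit and not the other. This stands.
- **Comparison 3 matters least.** It is last in the SAP's order and has no concurrent control, so it cannot carry an efficacy claim under either model. A reader might infer that the trial's main result is at risk. It is not, because the week-6 test in comparison 1 uses a different method and does not need the retention visit. This stands and limits the importance of the point.

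None of this defends discarding observed follow-up values when a method that keeps them is already in the SAP.

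**Conclusion.** The point holds in a limited form. As specified, comparison 3 uses only participants with all three visits: about 24 of 30 if 10% miss each later visit independently, 27 if the same people miss both. If missing retention depends on the observed response, completers overstate a true change of -1.0 by 0.11 to 0.36 at follow-up and 0.06 to 0.18 at retention. If it does not, there is no bias. These sizes rest on the assumed SD, correlation, missing rate and strength of dependence, none of which the documents give.

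It might also be inferred that the participant random effect named in comparison 2 could simply be carried over. It would be an improvement, but it keeps compound symmetry, a special case of the sphericity that the ANOVA assumes. It leaves part of the retention bias when correlations between visits differ.

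The change is worth making because it is cheap. Its importance is modest.

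**What to change.** In SAP section 1.1.1, replace the repeated measures ANOVA in comparison 3 with a likelihood-based mixed model for repeated measures that uses all available visits. Specify visit (categorical) and group as fixed effects, an unstructured within-participant covariance across the three visits, and a small-sample degrees-of-freedom correction such as Kenward–Roger.

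The cost is about one line of SAP text, with no new data or visits. There are two small downsides. The model relies on data being missing at random, so absence that depends on unobserved values would still need a sensitivity analysis. It also estimates six covariance parameters (three variances and three covariances) where a random intercept needs two, which is manageable with 30 participants and three visits.
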